#### Follow-up:

[figure not shown]
The last patient prospectively included will be followed for 2 years. All other patients will be followed until death or until the end of the follow-up of the last patient prospectively included.

Patients who started avelumab before the start of the study will be followed retrospectively, but also prospectively for those still alive at the beginning of the study.

Follow-up visits will be made during the course of regular visits and/or hospitalisations. No additional visits or examinations are required by the protocol, as the study is observational: follow-up and treatment modalities will be at the sole discretion of the participating physician. Clinical data will be collected every three months after the inclusion in the study and until death or the end of the study: 24 months after the inclusion of the last prospective patient. Patients initiating avelumab after the start of the study (prospective part of the study) will complete PRO questionnaires : 1) at the time of avelumab initiation, 2) at different time points after initiation if the patient is still treated with avelumab (6 weeks, 3 months, and every three months for up to 2 years, tumor progression if so), 3) and at avelumab discontinuation.

Number of sites: the study will be proposed to all sites participating to the ATU program, plus some additional centers expected to treat patients after the ATU period. Approximately 100 sites are expected to participate to the study.

Figure 1. Study design

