### 9.1.2. Secondary endpoints

- OS from the start of the chemotherapy used in 1st line: time between the first injection of the chemotherapy used in 1st line and the date of death from any cause.
- PFS1: time between the first injection of avelumab and the date of progression or death from any cause. Progression status will be defined according to RECIST 1.1.
- PFS2: time between the first injection of avelumab and the date of progression or death from any cause during the 2nd line of treatment post-avelumab. Progression status will be defined according to RECIST 1.1.
- ORR: proportion of patients with a Complete Response or Partial Response as a best response during the avelumab treatment. Responses to treatment will be defined according to RECIST 1.1.
- DOR: time between the beginning of the response and progression or death from any cause.
- DOT: time between the first and last dose of avelumab.
- Patterns of progression under avelumab: metastatic sites and type of progression (new lesion(s)/progression of known lesion(s)).
- Subsequent treatments and response to these treatments: DOT, PFS, ORR and OS.
- Safety: AEs of any type, grade 3-4 AEs, AEs leading to interruption or discontinuation, AEs leading to death.

090177e1a41aac13\Final\Final On: 28-Jul-2025 13:50 (GMT)

- Premedications (acetaminophen and antihistamine): Proportion of patients who received a premedication at each injection of avelumab. Median number of cycles with premedication. To evaluate the correlation between infusion-related reactions and premedication.
- Evolution of PROs NCCN/FACT FBISI-18 and EQ-5D-5L scores during avelumab treatment.

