Clinical Follow-up data	
 
• Avelumab administration               
 
. Date of each infusion, dose
 
. Use of premedication (acetaminophen and antihistamine)
 
 
 
• Tumoral response under avelumab               
 
. At inclusion (for retrospective data collection): tumoral evaluation (yes/no), best response since avelumab initiation, date of partial or complete response if so, date of progression if so with site(s) of progression and type (new or preexisting lesions).
 
. Tumoral evaluation since last visit (yes/no, date), response (partial remission, complete remission, progression, stable disease, not evaluable), site(s) of progression if so and type (new or preexisting lesions).
 
 
 
• ECOG if the patient is still on avelumab
 
• Avelumab discontinuation
 
	X		X

090177e1a41aac13\Final\Final On: 28-Jul-2025 13:50 (GMT)

	
 
. Temporary interruption(s) with reason and dates
 
. Permanent discontinuation with reason and date
 
• Subsequent treatments after avelumab discontinuation
 
. Regimen and dates start/discontinuation
 
. Best response, progression with date,
 
• Death with date and cause
 
• Lost to follow-up if so and date
 
• Date of withdrawal if so
 
			
Safety	Adverse events (see section 11)	X		X
Concomitant treatments	Corticosteroids/AIS/NSAIDs, sartans/ACE inhibitors, antibiotics, PPI, if the patient is still on avelumab	X		X
Patient reported outcome (PRO)	
Patients initiating avelumab after the start of the study will complete NCCN/FACT FBISI-18 and EQ-5D-5L questionnaires:
 
 
1) at the time of avelumab initiation (baseline)
 
2) at different time points after initiation if the patient is still treated with avelumab : 6 weeks, 3 months, every three months for up to 2 years, tumor progression if so
 
3) at avelumab discontinuation (whatever the reason is)
 
	X	X	X

\* In order to validate the type of variants, anonymized anatomical pathology reports of the patients concerned will be collected and reviewed by the steering committee.

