### **9.9.2. Measures taken to reduce patients lost to follow-up and missing data**

Data will be collected from medical chart, which may lead to incomplete or missing information. As this study will not influence or modify usual practices, investigators will have

the possibility to note "not done", "not known" or "not applicable" in the e-CRF, facilitating the quantification of missing data. In the event of missing data without one of these references being made, the CRA will endeavour to collect the corresponding information with the assistance of the investigator. However, if the data remain missing at the time of the analysis, they will not be replaced and will be treated as such.

In addition, the use of an e-CRF will limit data entry errors through automated online checks. Finally, training of the investigation teams to the e-CRF, as well as monitoring of data collection, will guarantee the quality of the information collected.

If patients are lost to follow-up, the investigators will agree to call patients, one of their family circles or their general practitioner, in order to recover enough data in order to close the file.

If any patients die, the doctor will investigate the cause of death.

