8.2.2.2 Progression free survival (PFS)

The PFS will be analyzed using survival analysis method, in the FAS, using the following table for censorship, and date of first study treatment intake as starting date.

Table 2: Event Date and Outcome for PFS

Scenario	Date of Event/Censoring	Outcome
Progression recorded before discontinuation of treatment	Progression date	Event
Death (without any previous recorded progression of treatment)	Death Date	Event
Final discontinuation of treatment during the study before any progression or death	Treatment Discontinuation Date	Censored
Lost to follow-up or early study discontinuation without progression or death	Last News Date	Censored

PFS will also be described by subgroup (See section 5.3 for subgroup definition).

8.2.2.3 Progression Free Survival (PFS) 2

For PFS 2, endpoint will be analyzed using a survival analysis, in the FAS, using the following table for censorship, and date of first study treatment intake as starting date. For this analysis, only participants who initiated a 2nd line post-avelumab systemic treatment will be considered. Local treatments as radiotherapy are not considered as second line post-avelumab.

Table 3: Event Date and Outcome for PFS

Scenario	Date of Event/Censoring	Outcome
Progression recorded during 2 nd line of post-avelumab treatment	Progression date	Event
Death (without any previous recorded progression of treatment) during 2 nd line of post-avelumab treatment	Death Date	Event
Final discontinuation of 2 nd line of post-avelumab treatment during the study before any progression or death	Treatment Discontinuation Date	Censored
Lost to follow-up or early study discontinuation without progression, death or 2 nd line of post-avelumab treatment discontinuation	Last News Date	Censored

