8.2.2.5 Duration of response (DOR)

For DOR, endpoint will be analyzed using a survival analysis, in the FAS, using the following table for censorship, and date of first response (Complete Response or Partial Response) as starting date.

Table 4: Event Date and Outcome for DORs

Scenario	Date of Event/Censoring	Outcome
Tumor assessment with a reported progressive disease, after response was observed.	Progression Date	Event
Death (whatever the cause) without treatment discontinuation	Death Date	Event
No reported progressive disease during the study nor death.	Last News Date	Censored
Lost to follow-up or early study discontinuation without stopping treatment	Last News Date	Censored
Treatment discontinuation	Discontinuation Date	Censored

DOR will also be described by subgroup (See section 5.3 for subgroup definition).

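### PFS, PFS2, subsequent-treatment PFS and DOR are censored at an undefined last-news date with no analysis at the last tumour assessment; where contact outlasts assessment, this biases them upwards

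*SAP*

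**What the plan says.** **Censoring rules.** In SAP 8.2.2.2, Table 2 (PFS), the row "Lost to follow-up or early study discontinuation without progression or death" is censored at the Last News Date. A separate row, "Final discontinuation of treatment during the study before any progression or death", is censored at the discontinuation date. Table 3 (PFS2, 8.2.2.3) and Table 6 (PFS of subsequent treatment, 8.2.2.9) follow the same pattern. In Table 4 (DOR, 8.2.2.5) two rows go to the Last News Date: "No reported progressive disease during the study nor death" and "Lost to follow-up or early study discontinuation without stopping treatment". Treatment discontinuation again has its own row.

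The SAP does not define Last News Date. No row of these tables, and no sensitivity analysis, uses the last tumour assessment. Table 2 has no row for a patient still on avelumab and progression-free at the cut-off.

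**How progression is established.** For PFS1 and PFS2, Protocol 9.1.2 states: "Progression status will be defined according to RECIST 1.1". No scan schedule is imposed. The follow-up text of Protocol 9.1 says that "follow-up and treatment modalities will be at the sole discretion of the participating physician".

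**What is collected.** At follow-up visits, Protocol 9.3 (Table 2) records "Tumoral evaluation since last visit (yes/no, date), response (partial remission, complete remission, progression, stable disease, not evaluable". For the retrospective period, the inclusion entry lists whether an evaluation took place, the best response, and dates of response and of progression only.

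**Loss to follow-up.** Protocol 9.9.2 says that "the investigators will agree to call patients, one of their family circles or their general practitioner", so that enough information is recovered to close the file.

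**Related rules.** OS is censored at the date of last contact (SAP 8.2.1, Table 1). SAP 5.3 classes a patient as a long responder when PFS reaches 12 months, whether or not an event was seen.

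**The concern.** A contact date suits OS, because any contact shows that the patient is alive. A RECIST progression can be recorded only when the tumour is assessed. If the last news comes after the last assessment, the patient stays in the Kaplan-Meier risk set for a period in which a death could be recorded but a progression could not. The denominator is kept up and the events are missing, so the curve is too high.

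The plan aims to confirm a randomised trial's effectiveness results in routine practice, and here the error favours the drug. It would affect the PFS and DOR curves and, through the 12-month threshold, membership of the long-responder group. That group is used for baseline characteristics and for OS and PFS subgroup analyses.

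**Working it through.** **1. A figure to reproduce.** The plan gives no expected PFS or DOR, loss rate or scan interval, so it has no figure on this point. Its only precision figure is for OS and does not bear on the question. Every input below that describes PFS, DOR, loss or scanning is an assumption. The sample size of 600 is the protocol's.

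**2. Mechanism.** The estimator is S(t) = ∏(1 − dᵢ/Yᵢ). For each patient censored at last news, the credited time is (last news date − last assessment date). During it the patient counts in Yᵢ but cannot add a progression to dᵢ. If last news falls before the next scan is due, the patient leaves the risk set before the next time at which progressions are found, so the product hardly changes. The bias needs contact that runs past a missed assessment.

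**3. Simulation on a regular scan schedule.** Inputs: 600 patients, 300 replicates, exponential PFS with median 6 or 9 months, scans every 2 or 3 months, loss hazard 0.5% to 2% per month, and stopping without progression 2% per month.

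- *Contact ends before the next scan is due.* At the final analysis 5% to 21% of patients are censored at last news and credited about 1.0 to 1.5 months each. The median and 12-month PFS change by 0.0.
- *Contact continues for 6 months without imaging.* Examples:

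| PFS median, scan interval, loss per month | Median PFS: last assessment → last news | 12-month PFS |
|---|---|---|
| 9 months, every 2 months, 0.5% | 9.97 → 10.18 (+0.2) | 39.6% → 40.8% (+1.2 points) |
| 6 months, every 3 months, 2% | 7.52 → 8.94 (+1.4) | 25.0% → 30.4% (+5.4 points) |
| 9 months, every 3 months, 2% | 10.44 → 11.92 (+1.5) | 39.5% → 44.4% (+4.9 points) |

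Over all settings with the 6-month tail, the change is +0.2 to +1.5 months in the median and +1.2 to +5.4 points at 12 months. For a DOR-like endpoint (median 18 months, loss 1% per month), the 24-month estimate goes from 40.1% to 42.5%, or +2.4 points.

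**4. Simulation with a variable gap.** Inputs: 600 patients, 200 data sets per gap, true median 6 months, scans about every 3 months, 25% lost.

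| Last news after last scan | Median: last assessment vs last news | 12-month PFS |
|---|---|---|
| 0 to 3 months | 7.56 vs 7.76 (+0.20) | 29.3% vs 30.1% (+0.8 points) |
| 0 to 6 months | 7.49 vs 7.90 (+0.41) | 29.1% vs 30.9% (+1.8 points) |
| 0 to 9 months | 7.48 vs 8.09 (+0.61) | 29.1% vs 32.1% (+3.0 points) |

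Both rules exceed 6 months mainly because progression is found only at the next scan (half of a 3-month interval is 1.5 months). That delay is not a censoring effect.

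**5. Each rule against complete follow-up.** Steps 3 and 4 compare the rules with each other and so do not show which is nearer the truth.

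- With a 6-month median, scans about every 3 months and 25% lost, last-news censoring errs by about +0.2 to +0.6 months as the gap grows from up to 3 to up to 9 months. Last-assessment censoring errs by a roughly constant −0.1 to −0.2 months.
- In a second set, 15% of first events were assumed to be deaths. For gaps of 0 to 3 months the median was 7.00 with complete follow-up, 6.83 with last assessment (−0.17) and 7.07 with last news (+0.07). For gaps of 0 to 6 months the errors were −0.26 and +0.31.
- With 5% lost, errors are about 0.1 month or less.

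The two sets agree on sign and on growth with the gap, but not on exact size.

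**6. Long-responder group.** A patient last scanned at 9 months with last news at 12.5 months is credited 12.5 − 9 = 3.5 months and crosses the 12-month line. Censored at 9 months, the patient does not.

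**7. Overlapping rows.** A patient who stops avelumab without progression and is later lost fits two rows of Table 2, with different dates. A responder who stops without progression or death fits two rows of Table 4. No precedence is stated.

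**The case against.** The strongest reply is that the exposure is narrow and the alternative rule is also biased.

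- Patients with a recorded discontinuation are censored at that date, so later contact is mostly not credited. The rule bears mainly on patients lost or leaving without a recorded stop and, in Table 4, on responders still on treatment. Their infusions are dated and their data are collected every three months. This stands, subject to the overlap in step 7.
- Last-assessment censoring counts deaths after the last scan as events but removes patients known to be alive at that scan, which pulls the estimate down. With gaps of at most 3 months, last news was the closer rule in one comparison. This stands, and is why both analyses should be reported.
- Assessment dates are not all available. A retrospective patient with stable disease has no listed assessment date for that period. Censoring such a patient at day 1 would discard time in which scans may have been done. This stands and shapes the fix.
- These are secondary endpoints in a purely descriptive study. This stands and limits the weight of the point.

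A reader might infer that last news is a phone call that shows only survival. The documents do not support that: the date is undefined, and Protocol 9.9.2 speaks of recovering enough data to close the file, which could include disease status. Nor do they show that scans were missing in the credited interval, since routine visits may include imaging. The objection does not remove the gap in the plan: the SAP neither prevents the condition for bias nor measures how often it occurs.

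**Conclusion.** The point holds in a conditional form. The four tables censor progression-based endpoints at an undefined date that need not coincide with a tumour assessment, and nothing in the SAP shows how much this matters. The direction is upwards wherever contact outlasts assessment.

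The size runs from about zero (last news before the next scan is due, or about 5% lost) to roughly +0.2 to +0.6 months in the median under an assumed 25% loss and gaps of up to 3 to 9 months. The larger differences in step 3 require 6 months of contact without imaging before last news. None of these inputs is in the documents.

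The overall OS estimate is unaffected. The OS comparison by long-responder status could be affected through group membership.

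Two stronger conclusions may tempt a reader: that PFS and DOR are materially inflated as planned, and that last-assessment censoring is unbiased. The documents do not support the first, and the comparison with complete follow-up contradicts the second.

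**What to change.** 1. Define Last News Date for these endpoints, including which kinds of contact count.
2. In Tables 2, 3, 4 and 6, censor patients without progression or death at the last evaluable tumour assessment where a date exists. Report last-news censoring alongside as a sensitivity analysis.
3. For retrospective patients with no recorded assessment date, retrieve the last scan date from the chart or state a fallback, for example the last documented on-treatment visit. Do not default to day 1.
4. Add a Table 2 row for patients progression-free on treatment at the cut-off, and state which row takes precedence when two apply.
5. Report the distribution of the time from last assessment to last news.
6. State which censoring date feeds the 12-month long-responder rule.

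The cost is mostly SAP wording and one extra set of estimates, plus some chart retrieval. The downsides are slightly shorter follow-up, slightly less favourable PFS and DOR, and the small downward bias of last-assessment censoring.

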6 ENDPOINTS AND COVARIATES

6.1 EFFICACY/EFFECTIVENESS ENDPOINT(S)

6.1.1 Time-to-event endpoints

Variable	Role	Data source(s)	Operational definition
Overall Survival (OS)	Time to Event Outcome (primary endpoint)	Patient medical records and CRF	Time (month) from the first injection of avelumab to death, whatever the reason +1
Overall Survival 2	Time to Event Outcome (secondary endpoint)	Patient medical records and CRF	Time (month) from the first injection of the chemotherapy used in 1st line to death, whatever the reason +1
Progression Free Survival (PFS)	Time to Event Outcome (secondary endpoint)	Patient medical records and CRF	Time (month) from the first injection of avelumab to the date of progression or death from any cause +1.
Progression Free Survival (PFS) 2	Time to Event Outcome (secondary endpoint)	Patient medical records and CRF	Time (month) from the first injection of avelumab to the date of progression or death from any cause during the 2nd line of treatment post-avelumab +1.
Objective Response Rate (ORR)	Outcome (secondary endpoint)	Patient medical records and CRF	Proportion of patients with a Complete Response (CR) or Partial Response (PR) as a best response during the avelumab treatment.
Duration Of Response uber avelumab (DOR)	Time to Event Outcome (secondary endpoint)	Patient medical records and CRF	Time (month) from the beginning of the response to progression or death from any cause + 1.
Duration Of	Time to Event	Patient medical	Time (month) from the first to last dose of avelumab + 1.

PFIZER CONFIDENTIAL

CT24-WI-GL03-RF02 2.0 Non-Interventional Statistical Analysis Plan For Primary Data Collection Study

01-Jun-2020

Page 12 of 28

Treatment (DOT)	Exposure	records and CRF	
Patterns of progression under avelumab	Outcome (secondary endpoint)	Patient medical records and CRF	Description of metastatic sites and type of progression (new lesion(s)/progression of known lesion(s)).
OS of subsequent treatment	Time to Event Outcome (secondary endpoint)	Patient medical records and CRF	Time (month) from the first injection of avelumab-subsequent treatment to death, whatever the reason +1

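### PFS2 is timed from first avelumab injection but analysed only in patients who later start another systemic line, so it describes next-line starters and not the Full Analysis Set

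*SAP*

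**What the plan says.** - **Time origin and population.** SAP 8.2.2.3 places PFS2 in the FAS with the "date of first study treatment intake as starting date". It then states: "For this analysis, only participants who initiated a 2nd line post-avelumab systemic treatment will be considered". It adds: "Local treatments as radiotherapy are not considered as second line post-avelumab". SAP 5.1 defines the FAS as every enrolled patient with at least one avelumab injection, and the summary table in SAP 8.2.5 lists PFS 2 under FAS.
- **Definition.** SAP 6.1.1 measures time "from the first injection of avelumab to the date of progression or death from any cause during the 2nd line of treatment post-avelumab". Protocol 9.1.2 has the same substance: "PFS2: time between the first injection of avelumab and the date of progression or death from any cause during the" second line after avelumab. Neither definition states a restricted population.
- **Events and censoring.** SAP Table 3 counts progression or death during that line. It censors at "Final discontinuation of 2 nd line of post-avelumab treatment during the study before any progression or death". It has no row for a death before the line starts or for a patient who never starts one.
- **Objective.** Protocol section 8 and SAP 2.2 both list estimating PFS2 as a secondary objective, for the overall population.

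**The concern.** The clock starts at avelumab, but membership is decided later by whether a further systemic line was started. Three things follow from the text alone.

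1. A patient who dies without a further line has failed on any ordinary reading of PFS2, yet is removed.
2. A patient still controlled on avelumab at the cut-off has one of the best outcomes, yet is removed.
3. Nobody who is kept can have an event before the next line begins, so that interval is immortal time.

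The SAP recognises this hazard two sections earlier: 8.2.2.1 uses left truncation for OS from chemotherapy start, expressly to avoid immortal time bias. PFS2 has no equivalent protection.

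At stake is a published PFS2 that carries the FAS label and would be read as the experience of avelumab-treated patients. SAP section 3 plans yearly analyses for publication, and the included set changes at each cut-off, so successive reports could show PFS2 moving when nothing about the patients has changed.

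**Working it through.** **The plan's own figures.** The documents give no figure for PFS2. The only design figure is OS precision in protocol 9.5. With mean 29 months, the median is 29 × ln 2 = 20.1, and the exact limits are 20.1 × 2n/χ²(0.975; 2n) and 20.1 × 2n/χ²(0.025; 2n). For n = 600 this gives [18.59; 21.81] (stated [18.6; 21.8]); for n = 47 it gives [15.40; 27.36] (stated [15.4; 27.4]). Both reproduce, and neither bears on PFS2.

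**What happens to each type of patient**

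| Course after first avelumab injection | Natural PFS2 status | Under SAP 8.2.2.3 |
|---|---|---|
| Starts next line, progresses or dies on it | Event | Included, event |
| Starts next line, event-free at cut-off | Censored | Included, censored |
| Dies with no further systemic line | Event | Excluded |
| Still controlled on avelumab | Censored, long time | Excluded |
| Stopped avelumab, alive, no systemic line (including radiotherapy only) | Censored | Excluded |

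Excluding the third row lengthens PFS2. Excluding the fourth shortens it, most strongly when follow-up is short. The net sign is therefore not fixed by the text.

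**Illustration (all inputs assumed)**

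- Time to progression on avelumab, P: exponential with rate ln 2/median; 25% of patients have median 40 months, 75% have median 5.
- 30% of progressors die without a next line, at P + D, with D exponential and median 1, 2 or 3 months.
- The others start the next line at P + 1 month and have their PFS2 event at P + 1 + X, with X exponential and median 4 months.
- Censoring C is uniform over 24-54 months (final) or 6-18 months (early interim). The final range is plausible: 24 months is the planned minimum, and July 2020 (ATU) to the end of 2024 is about 54. The interim range resembles IA1: started at least 6 months before 31 January 2022, and at most about 19 months before it.
- All FAS: Kaplan-Meier on min(event, C). Starters only: the same times and indicators, keeping only patients with next-line start ≤ C. Table 3's censoring at next-line discontinuation is not modelled, so the contrast isolates the population restriction.

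Results with 400,000 simulated patients per scenario; ranges cover D = 1 to 3 months:

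| Scenario | Quantity | Starters only | All FAS |
|---|---|---|---|
| Final | 24-month rate | 17% | 26-27% |
| Final | Median, months | 12.7 | 12.9-13.9 |
| Interim, 6-18 months | Median, months | 9.9 | 12.9-13.9 |
| Interim, 6-18 months | 12-month rate | 38% | 53-57% |
| No long-PFS group, 40% die without next line (final) | Median, months | about 11.8 | 9.6-10.9 |

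**Cut-off dependence.** With identical true outcomes, the starters-only median goes from 9.9 months at the interim to 12.7 at the final analysis, a shift of 2.8. The all-FAS median is 12.9-13.9 at both.

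**Wider range.** The inputs were varied: median avelumab control 4-9 months, 15-45% dying without a next line, median next-line control 3-6 months, up to 35% long-controlled, follow-up 24-42 months. The restriction then keeps 44-85% of patients (about 262 to 507 of 600). The change in median runs from 12.08 − 14.33 = −2.25 months to 13.21 − 9.12 = +4.09 months.

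**The case against.** The strongest reply is that the restriction follows from the protocol. Protocol 9.1.2 and SAP 6.1.1 already tie the event to the second line after avelumab, so Table 3 largely puts the protocol into operation. The restriction is stated openly. PFS2 is one of many secondary endpoints in a study that SAP 4.2 calls purely descriptive. The excluded patients still count in OS and in PFS from avelumab start.

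Much of this stands. It limits the severity, and it means the correction cannot be confined to the SAP. It does not rescue the analysis: neither definition says that patients without the line are left out, and a result limited to starters contradicts the FAS label in 8.2.2.3 and 8.2.5.

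Three stronger readings are tempting and should be resisted.

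- A reader might infer that the result applies to no identifiable population. It does apply to one, namely participants who started a further systemic line; the problem is that this group is defined after time zero and labelled FAS.
- A reader might infer that the rule flatters avelumab, or that it penalises it. The sign depends on proportions the documents do not give.
- A reader might take the early-interim gap as typical of every yearly analysis. Later cut-offs have longer follow-up, and at the final analysis the median differs by only about 0.2 to 1.2 months in the main scenario.

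There is also an ambiguity. The second line post-avelumab could mean the line directly after avelumab or the one after that. SAP 8.2.2.8 defines only subsequent treatment, as the line following avelumab maintenance. The illustration takes the first meaning.

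**Conclusion.** The concern holds as a secondary-endpoint correction. As written, SAP 8.2.2.3 does not estimate PFS2 of avelumab-treated patients. It gives a starters-only curve containing immortal time, biased relative to the FAS in a direction that cannot be known beforehand and dependent on the cut-off. That conclusion rests on the text and needs no assumed number.

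The size does rest on assumptions, including the 1 to 3 months' median from progression to death without a next line. In the main scenario the late part of the curve is affected most: the final 24-month rate falls by 9 to 10 percentage points, while the median changes little. With no long-PFS group and 40% dying without a next line, the restriction instead lengthens the median by roughly 1 to 2 months. Primary OS and the sample size are unaffected.

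**What to change.** - **Population and origin:** analyse PFS2 in all FAS patients from first avelumab injection and delete the restriction to next-line starters.
- **Events:** progression on the next systemic line, or death from any cause, including death before any next line.
- **Censoring:** at last contact for everyone without an event, including patients still on avelumab and those with no next line. State explicitly that this replaces Table 3's censoring at next-line discontinuation.
- **Definition of the line:** define the second line post-avelumab as the systemic line directly after avelumab, consistent with SAP 8.2.2.8.
- **Alignment:** bring protocol 9.1.2, SAP 6.1.1 and SAP 8.2.2.3 with Table 3 into the same wording.
- **Starters-only result:** if kept, label it as such and not as FAS. SAP 8.2.2.9 already describes next-line PFS with the clock starting at that line. Left truncation at next-line start would remove the immortal time but would not restore the excluded patients.

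The cost is aligned wording in protocol and SAP and the reprogramming of one endpoint. No new data are needed: subsequent regimens with dates, progression and death are already collected (protocol 9.3, Table 2).
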